### **9.3 SELECTION OF STUDY POPULATION**

#### **9.3.1 Inclusion Criteria**

Patients must provide assent to participate and their LAR and caregiver (even if the same as the LAR) must provide written informed consent prior to the conduct of any study-specific procedures (see also [Section 5.3](#)).

To be eligible to participate in the study, patients must meet the following criteria:

1. Male or female outpatients between 12-17 years of age, inclusive, at Visit 1
2. Patients must meet DSM-IV-TR criteria for MDD, confirmed by K-SADS-PL
3. Patients must have a score  $\geq 40$  on the Children's Depression Rating Scale-Revised (CDRS-R) at Visits 1 and 2
4. Patients must have a Clinical Global Impressions-Severity (CGI-S) score  $\geq 4$  at Visits 1 and 2
5. Patients must have a caregiver who can and is willing to consent to be responsible for safety monitoring of the patient, provide information about the patient's condition, oversee the administration of investigational product, and accompany the patient to all study visits (see Section 5.3)
6. Patients must have normal physical examination findings, vital sign values, clinical laboratory test results, and electrocardiogram (ECG) results or abnormal results that are judged not clinically significant by the Investigator
7. Female patients must have a negative serum  $\beta$ -human chorionic gonadotropin ( $\beta$ -hCG) pregnancy test result at Visit 1

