#### **9.7.5.1 Primary Efficacy Parameter**

The primary efficacy parameter is the change from baseline to end of Week 8 in the CDRS-R total score. The primary analysis will be performed using an MMRM with treatment group, study center, visit, and treatment group-by-visit interaction as the fixed effects and the baseline value and baseline value-by-visit interaction as the covariates. An unstructured covariance matrix will be used to model the covariance of within-patient scores. The Kenward-Roger approximation ([Kenward and Roger, 1997](#)) will be used to estimate denominator degrees of freedom. This analysis will be performed based on all postbaseline scores using only the observed cases without imputation of missing values. The multiple comparison issues will be addressed using the matched parallel gatekeeping procedure ([Chen et al, 2005](#)).

In addition, 2 sensitivity analyses, LOCF and pattern-mixture model, will be performed on the primary efficacy parameter. For the LOCF approach, the between-treatment group comparison will be performed by means of an analysis-of-covariance model with treatment group and pooled study center as factors and the baseline CDRS-R total score as the covariate. The LOCF approach will be used to impute missing postbaseline values, provided that at least 1 postbaseline assessment is available. Missing values between the baseline and the first nonmissing postbaseline will be imputed with the baseline value. If all the postbaseline values are missing, baseline value will not be carried forward. Only the total score of a parameter will be imputed using the LOCF approach; individual item scores will not be carried forward.

In the other sensitivity analysis, a pattern-mixture model based on non-future dependent missing value restrictions ([Kenward et al, 2003](#)) will be performed to assess the robustness of the primary MMRM results to the possible violation of the missing-at-random missingness assumption. The non-future dependent missing value restriction states that the probability of drop-out at a specific visit can only depend on the observed value and the possibly missing value up to that visit, but not future values beyond that visit. The details of this sensitivity analyses are as follows:

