Exposure to the investigational product for the Safety Population during the double-blind treatment period will be summarized in terms of treatment duration, calculated as the number of days from the date of the first dose of double-blind investigational product to the date of the last dose of double-blind investigational product during the double-blind treatment period, inclusive. Descriptive statistics (number of patients, mean, SD, median, minimum, and maximum) will be presented by treatment group. The number and percentage of patients will be presented for specific intervals of exposure by treatment group.

Patient-years, defined as total exposure to double-blind investigational product in years (excluding the double-blind down-taper period), will be summarized by treatment group for the Safety Population.

In addition, weekly and overall mean daily dose of investigational product during the double-blind treatment period will be summarized by treatment group for the Safety Population.

9.2

MEASUREMENT OF TREATMENT COMPLIANCE

Dosing compliance for a specified period is defined as the number of capsules actually taken by a patient during that period divided by the number of capsules prescribed for the same period multiplied by 100. The total number of capsules actually taken during a specific time period will be calculated from the study medication records. The number of capsules expected to be taken for a specific treatment period will be calculated by multiplying the number of days in that period by the number of capsules prescribed to be taken per day.

Descriptive statistics for investigational product compliance during the double-blind treatment period will be presented by treatment group for each period between 2 consecutive visits, as well as for the whole double-blind treatment period, for the Safety Population.

10.0

EFFICACY ANALYSES

The efficacy analyses will be based on the ITT Population. *Baseline* for each efficacy parameter is defined as the last nonmissing assessment before the first dose of double-blind investigational product. All statistical tests will be 2-sided hypothesis tests performed at the 5% level of significance for main effects. All confidence intervals will be 2-sided 95% confidence intervals, unless stated otherwise.

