10.1 PRIMARY EFFICACY PARAMETER

The primary efficacy parameter is the change from baseline to Week 8 in CDRS-R total score. The primary analysis for comparing levomilnacipran 40 mg vs. placebo, and levomilnacipran 80 mg vs. placebo for the primary efficacy parameter will be performed using an MMRM with treatment group, pooled study center, visit, and treatment group-by-visit interaction as fixed effects and the baseline value and baseline value-by-visit interaction as covariates. An unstructured covariance matrix will be used to model the covariance of within-patient scores. The Kenward-Roger approximation ([Kenward and Roger, 1997](#)) will be used to estimate denominator degrees of freedom. This analysis will only use the observed cases of postbaseline scores without imputation of missing values. To control the overall type I error rate for the multiple comparisons across the primary and the secondary hypotheses, the matched parallel gatekeeping procedure ([Chen et al., 2005](#)) will be applied. Details are provided in Section 10.2.

Graphical display of treatment difference vs. placebo (mean difference \pm SE) in primary efficacy parameter will be provided by study center.

In addition, two sensitivity analyses, LOCF and pattern-mixture model approaches, will be performed on the primary efficacy parameter.

The LOCF approach is based on an analysis-of-covariance (ANCOVA) model including treatment group and pooled study center as factors and baseline CDRS-R total score as a covariate. The pattern-mixture model approach is based on the non-future dependent missing value restrictions ([Kenward et al., 2003](#)) and is performed to assess the robustness of the primary MMRM results to the possible violation of the missing-at-random assumption. The details of this sensitivity analysis are as follows:

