Original sample size calculation: the effect size (treatment group difference relative to pooled standard deviation) of **0.36** for both levomilnacipran and fluoxetine is based on a treatment difference of **4 units** with a common pooled standard deviation of **11.1** for the primary efficacy parameter, change from baseline to Week 8 in CDRS-R total score. Adjusting for multiple comparisons of two levomilnacipran groups with placebo across the primary and secondary endpoints by using the matched parallel gatekeeping procedure, a sample size of **660** patients (**165** per treatment group) will provide 85% power for the primary analysis (levomilnacipran vs. placebo) and for assay sensitivity analysis (fluoxetine vs. placebo) based on an MMRM model using simulation method (Lu, 2012). The simulation assumed a correlation of 0.7 between the repeated measures, and a dropout rate of 17%, based on historical data in pediatric patients.

Sample size recalculation based on discussion with FDA: following the discussion with FDA, the study will be deemed as successful if statistical significance is achieved in at least one of two levomilnacipran doses (40 mg/day and 80 mg/day) versus placebo based on the primary efficacy endpoint. Therefore, resultant sample size is **520** patients (**130** per treatment group) as required by 85% power based upon statistical significance in at least one of the two dose levels with the same effect size assumption.

[figure not shown]

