Sample size recalculation based on interim analysis: following a blinded interim analysis, the sample size has been re-estimated. The MMRM model to estimate the pooled variance for change from baseline in CDRS-R total score at Week 8 includes pooled study site and week as factors and baseline CDRS-R total score and baseline value-by-week interaction as covariates, where week is included as a class variable. A total of 421 patients were included in the ITT analysis. Of these 421 patients, 347 (82.4%) patients have observed data at Week 8, so the estimated drop-out rate at Week 8 is 17.6%. Based on the MMRM model, the variance estimate for the change from baseline in CDRS-R total score at Week 8 is 129.53, and the estimated pooled standard deviation is 11.38. Thus the estimated effect size is 0.35 based on a treatment difference of 4 units and a pooled standard deviation of 11.38. Assuming an effect size of **0.35**, a common dropout rate of **17.6%**, and a correlation of 0.7 between the repeated measures, an estimated total sample size of **544** patients (**136** per treatment group) will be needed to maintain the 85% power to detect the treatment difference of 4 units for at least one levomilnacipran group versus placebo and for fluoxetine versus placebo.

15.0

STATISTICAL SOFTWARE

Statistical analyses will be performed using

[REDACTED]

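### The primary model leaves the Visit 1 CDRS-R score unused; adding it as a second covariate is valid and nearly free, but the gain could be anything from nothing to about a sixth of the residual variance

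*SAP*

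**What the plan says.** Protocol 9.3.1, criterion 3, sets a minimum CDRS-R score of 40 at two visits: "CDRS-R) at Visits 1 and 2". Criterion 4 does the same for CGI-S, with a minimum of 4. Each eligible patient therefore has two pre-treatment ratings on the primary and the secondary scale.

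SAP 10.0 takes a single baseline, which "is defined as the last nonmissing assessment before the first dose of double-blind investigational product". Protocol 9.7.5 anchors baseline to Visit 2 or, failing that, an earlier value. In practice this is the Visit 2 score.

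The primary MMRM in SAP 10.1 has treatment, pooled centre, visit and treatment-by-visit as fixed effects, with "the baseline value and baseline value-by-visit interaction as covariates". Protocol 9.7.5.1 has the same covariates: "the baseline value and baseline value-by-visit interaction as the covariates". Both say that only observed postbaseline scores are analysed. The Visit 1 score therefore enters neither as a covariate nor as a response.

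On size, SAP 14.0 reports from the blinded interim model that "the estimated pooled standard deviation is 11.38" and concludes that 544 patients "will be needed to maintain the 85% power to detect the treatment difference of 4 units for at least one levomilnacipran group versus placebo". That interim model already contained one baseline score and its interaction with week.

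**The concern.** A single clinician rating measures underlying severity with error. A second rating taken before randomisation can explain part of the Week 8 variation that the first leaves in the residual. Adjusting for it cannot bias the treatment comparison. Here the rating is required by the entry criteria and then dropped from the model.

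The plan's own history shows what a few percent of variance is worth. The SD moved from 11.1 to 11.38, so the variance rose from 123.21 to 129.53, or 5.1%. Together with dropout moving from 17% to 17.6%, that took the trial from 520 to 544 patients, while protocol 9.7.8 notes that recruitment is difficult. A covariate that recovers about 5% would be worth roughly as much as those 24 patients.

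**Working it through.** **Inputs from the documents.** Two-sided 5% tests (SAP 10.0); difference 4, SD 11.38, dropout 17.6%, correlation 0.7 between repeated measures, 136 per arm (SAP 14.0); weighted Simes with weights 0.5 and 0.5 on the two doses (SAP 10.2); success if either dose wins (SAP 14.0).

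**Assumed, because the documents are silent.** The correlations of Visit 1 with Week 8 (r1), Visit 2 with Week 8 (r2), and Visit 1 with Visit 2 (r12); five postbaseline visits, with dropout spread evenly over them.

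**Step 1: reproduce the plan's figure.** With correlation 0.7 and 17.6% monotone dropout, the MMRM information at Week 8 is that of 124.9 patients per arm. The standard error is 11.38 × √(2/124.9) = 1.44. Success means one p-value at or below 0.025 or both at or below 0.05, with two tests sharing the placebo arm. Simulation gives 85.7% power at 544, and 85% is reached at 134 per arm, or 536. The stated 544 for 85% is reproduced to within 2%. Using four or six visits moves power by less than 0.3 points.

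**Step 2: effect of adding Visit 1.** Because Visit 2 is already a covariate, the residual is the same whether the response is the Week 8 score or the change from Visit 2. The ratio of new to old residual variance is

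1 − (r1 − r2·r12)² / [(1 − r12²)(1 − r2²)].

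- All 0.7: 1 − (0.7 − 0.49)²/(0.51 × 0.51) = 1 − 0.0441/0.2601 = 0.830
- r1 = r2 = 0.5, r12 = 0.7: 1 − 0.0225/0.3825 = 0.941
- r1 = r2 = 0.3, r12 = 0.7: 1 − 0.0081/0.4641 = 0.983
- r1 = 0.6, r2 = r12 = 0.7: 1 − 0.0121/0.2601 = 0.953
- r1 = r2 × r12: the numerator is zero, so the ratio is 1

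Both scores are cut off at 40. Simulating 0.7 throughout with an assumed pre-selection mean of 50 and SD of 10, and keeping patients at 40 or above at both visits, gives r12 = 0.587, r1 = 0.590, r2 = 0.591 and a ratio of 0.861. Assumed means of 45 and 55 give 0.876 and 0.847.

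**Step 3: carry through.** The 11.38 is already adjusted for one baseline, so the ratio applies to it directly. Effective n is held at 124.9, which is an approximation. Equivalent N is 544 × ratio: the number that, with both covariates, matches the precision of 544 with one.

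| r1 / r2 / r12 | Ratio | SD | SE | Power at 544 | Equivalent N |
|---|---|---|---|---|---|
| 0.7 / 0.7 / 0.7 | 0.830 | 10.37 | 1.31 | 91.4% | 452 |
| same, gated at 40 | 0.861 | 10.56 | 1.34 | 90.5% | 468 |
| 0.5 / 0.5 / 0.7 | 0.941 | 11.04 | 1.40 | 87.8% | 512 |
| 0.6 / 0.7 / 0.7 | 0.953 | 11.11 | 1.41 | between its neighbours | 519 |
| 0.4 / 0.4 / 0.7 | 0.966 | 11.19 | 1.42 | 86.9% | 526 |
| 0.3 / 0.3 / 0.7 | 0.983 | 11.28 | 1.43 | 86.3% | 534 |
| r1 = r2 × r12 | 1.000 | 11.38 | 1.44 | 85.7% | 544 |

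The choice of r12 matters too. At 0.6 and 0.8 in place of 0.7, the ungated cut is 24% and 11% with r1 = r2 = 0.7, 8% and 4% with 0.5, and 2% and 1% with 0.3.

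**The case against.** The case for leaving the model alone is a serious one. It is a standard, valid baseline-adjusted MMRM, and 544 was sized with the same single-baseline adjustment, so nothing promised is lost. That stands. A reader might infer that the trial is underpowered or the primary test biased; Step 1 shows neither follows.

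The gain may be nil. Visit 1 lies one to five weeks further from Week 8 than Visit 2 does, so a lower correlation is natural, and dropping r1 from 0.7 to 0.6 removes most of the headline gain. This also stands. The exact zero does require special conditions. If true severity decays over time and each rating has reliability L below 1, then r1 − r2·r12 is proportional to L(1 − L), which is positive. With assumed L = 0.8 and weekly decay 0.95 (one week, then eight), r12 = 0.760, r2 = 0.531 and r1 = 0.504, and the cut is 0.0102/0.3034, or about 3%.

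A reader might infer that the plan's own 0.7 guarantees a 14% to 17% cut. It does not: 0.7 is stated for the repeated measures in the sample-size simulation, and nothing extends it to screening scores. A reader might also take Visit 2 as the gated score and Visit 1 as a clean alternative. Visit 1 is gated at the same 40, and rating inflation common to both visits would add no information.

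The practical objections are fair but small. Screening assessments can be repeated, an ITT patient could lack a Visit 1 score, and the protocol states the primary model too. Short rules deal with these.

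**Conclusion.** The omission is plain in both documents: a pre-randomisation rating on the primary scale, required for entry, is not used in the primary model. It costs possible precision, not validity. With r12 at 0.7, the residual variance cut ranges from zero to about 17%, and any-dose power at 544 from 85.7% to 91.4%. Where in that range the trial lies cannot be settled from the documents, because it depends on three correlations that they do not report and, for the gated figures, on an assumed score distribution. A gain of a few percent is enough to justify a change this cheap. No gain has been computed for CGI-S.

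**What to change.** Before unblinding, amend SAP 10.1:

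- Add the Visit 1 CDRS-R total and its interaction with visit, beside the Visit 2 baseline, in the primary MMRM and the Site 054 MMRM.
- Add the Visit 1 total to the LOCF ANCOVA and to the final ANCOVA of the pattern-mixture analysis. The imputation steps in Appendix I can stay as they are.
- Keep change from the Visit 2 baseline as the endpoint.
- Define the Visit 1 score as the first screening rating. Replace any missing Visit 1 score with the mean pooled over all arms, so that no ITT patient is lost.

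The size of the gain can be checked first without treatment codes. Refit the pooled interim MMRM (421 patients, 347 with Week 8 data) with the Visit 1 score and its interaction with week, and compare the Week 8 variance with 129.53. If the reduction is negligible, record that and leave the model unchanged.

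The same change with Visit 1 CGI-S in SAP 10.2 is an optional parallel.

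Cost: one extra coefficient per postbaseline visit, and an entry in SAP 17.0 documenting the departure from protocol 9.7.5.1. No new data are needed. The gain may be close to zero for patients whose Visit 1 rating came before washout of earlier medication, but the adjustment introduces no bias.

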10.2 SECONDARY EFFICACY PARAMETER

The secondary efficacy parameter is the change from baseline to Week 8 in CGI-S score, which will be analyzed using the MMRM approach similar to the one used for the primary efficacy parameter. A sensitivity analysis will also be performed using the LOCF approach as described in Section 10.1.

[figure not shown]
To control the overall type I error rate for multiple comparisons across the primary and the secondary efficacy parameters and multiple doses, the matched parallel gatekeeping procedure (Chen et al., 2005) will be implemented. The primary hypotheses family, F_1 , consists of 2 null hypotheses H_{11} and H_{12} which are for comparisons of levomilnacipran 40 mg and 80 mg, respectively, with placebo in regard to the primary efficacy parameter, change from baseline to Week 8 in CDRS-R total score. Similarly for the secondary efficacy parameter, change from baseline to Week 8 in CGI-S score, we have the corresponding hypotheses family $F_2 = \{H_{21}, H_{22}\}$. Family F_1 will serve as the parallel gatekeeper for F_2 . Then the matched gatekeeper procedure utilizes the special logical relationship between the primary and the secondary parameters to enhance the power of statistical testing, i.e., primary and secondary hypotheses are matched on dose. The secondary efficacy parameter will be tested at a specific dose only if the corresponding primary efficacy parameter is statistically significant. Weighted Simes test will be performed to derive the local p-values for the intersection hypotheses. Assignment of weight for all $2^4 - 1 = 15$ intersection hypotheses is shown in Table 10.2–1.

[figure not shown]
Table 10.2–1. Weights for Intersection Tests in the Matched Parallel Gatekeeping Procedure

Intersection hypothesis	Weight			
	H_{11}	H_{12}	H_{21}	H_{22}
$H_{11} \cap H_{12} \cap H_{21} \cap H_{22}$	0.5	0.5	0	0
$H_{11} \cap H_{12} \cap H_{21}$	0.5	0.5	0	0
$H_{11} \cap H_{12} \cap H_{22}$	0.5	0.5	0	0
$H_{11} \cap H_{12}$	0.5	0.5	0	0
$H_{11} \cap H_{21} \cap H_{22}$	0.5	0	0	0.5
$H_{11} \cap H_{21}$	1	0	0	0
$H_{11} \cap H_{22}$	0.5	0	0	0.5
H_{11}	1	0	0	0
$H_{12} \cap H_{21} \cap H_{22}$	0	0.5	0.5	0

$H_{12} \cap H_{21}$	0	0.5	0.5	0
$H_{12} \cap H_{22}$	0	1	0	0
H_{12}	0	1	0	0
$H_{21} \cap H_{22}$	0	0	0.5	0.5
H_{21}	0	0	1	0
H_{22}	0	0	0	1

The adjusted p-values for the four elementary hypotheses will be calculated from the local p-values based on the closed testing principle. Statistical significance is determined by comparing the adjusted p-values to $\alpha = 0.05$. The multiplicity method controls the family-wise type I error rate since the Simes inequality holds for multivariate normal distributions with nonnegative correlations ([Sarkar, 2008](#)). The large sample size of this study ensures asymptotic normality while nonnegative correlations are well-known among different active versus placebo comparisons and are expected to exist across different time points and between the CDRS-R and CGI-S endpoints based on historical data.

11.1 ADVERSE EVENTS

Adverse events will be coded by system organ class and preferred term using the Medical Dictionary for Regulatory Activities, version 16.1 or newer.

[figure not shown]
An AE (classified by preferred term) that occurs during the double-blind treatment period or during the double-blind down-taper period will be considered a treatment-emergent adverse event (TEAE) if it was not present before the date of the first dose of double-blind investigational product, or was present before the date of the first dose of double-blind investigational product and increased in severity during the double-blind treatment period or during the double-blind down-taper period, respectively. If more than 1 AE was reported before the date of the first dose of double-blind investigational product and coded to the same preferred term, the AE with the greatest severity will be used as the benchmark for comparison with the AEs occurring during the double-blind treatment period or during the double-blind down-taper period that were also coded to that preferred term. An AE that occurs more than 30 days after the date of the last dose of double-blind investigational product in the study will not be counted as a TEAE but will be included in the listings.

[figure not shown]
An AE occurring during the double-blind down-taper period will be considered a newly emergent AE (NEAE) if it is not present before the start of the double-blind down-taper period or was present before the start of the double-blind down-taper period but increased in severity during the double-blind down-taper period. The NEAEs during the double-blind down-taper period will be summarized by body system, preferred term, and treatment group for all patients who enter the double-blind down-taper period.

[figure not shown]
The number and percentage of patients reporting TEAEs in each treatment group will be tabulated by system organ class and preferred term and further categorized by severity and causal relationship to the investigational product, for both the double-blind treatment period and the double-blind down-taper period, separately. If more than 1 AE is coded to the same preferred term for the same patient, the patient will be counted only once for that preferred term using the greatest severity and strictest causality for the summarization by severity and by causal relationship to the investigational product, respectively.

[figure not shown]
The distribution of TEAEs by severity and causal relationship to the investigational product will be summarized by treatment group separately for the double blind treatment period and the double-blind down-taper period. Common TEAE during the double-blind treatment period is defined in 2 ways: $\geq 1\%$ of patients in any treatment group and $\geq 2\%$ of patients in any treatment group. The incidence of common TEAEs will be summarized separately by preferred term, and treatment group and will be sorted by decreasing frequency for the levomilnacipran treatment group (first levomilnacipran 80 mg/day, then levomilnacipran 40 mg/day).

[figure not shown]
A serious adverse event (SAE) that occurred between the date of the first dose of double-blind investigational product and 30 days after the date of the last dose of double-blind investigational product, inclusive, will be considered an on-therapy SAE.

12.0

HEALTH OUTCOMES ANALYSES

Not applicable.

13.0

BLINDED INTERIM ANALYSIS

A blinded interim analysis will be conducted when approximately 75% of randomized patients have either completed the study or discontinued from the study. The blinded interim analysis is to obtain an estimate of the pooled standard deviation of the change from baseline to Week 8 in the CDRS-R total score. If the estimated pooled standard deviation is larger than the assumed pooled standard deviation specified in Determination of Sample Size (Section 14.0), the sample size may be increased to ensure an adequate power. However, due to the difficulties in recruiting pediatric patients with MDD, the total number of patients of the study will be capped at **800 (200 per treatment group)**. Detailed specification of the blinded interim analysis will be provided in the blinded interim analysis plan, a separate document.

14.0

DETERMINATION OF SAMPLE SIZE

Original sample size calculation: the effect size (treatment group difference relative to pooled standard deviation) of **0.36** for both levomilnacipran and fluoxetine is based on a treatment difference of **4 units** with a common pooled standard deviation of **11.1** for the primary efficacy parameter, change from baseline to Week 8 in CDRS-R total score. Adjusting for multiple comparisons of two levomilnacipran groups with placebo across the primary and secondary endpoints by using the matched parallel gatekeeping procedure, a sample size of **660** patients (**165** per treatment group) will provide 85% power for the primary analysis (levomilnacipran vs. placebo) and for assay sensitivity analysis (fluoxetine vs. placebo) based on an MMRM model using simulation method (Lu, 2012). The simulation assumed a correlation of 0.7 between the repeated measures, and a dropout rate of 17%, based on historical data in pediatric patients.

Sample size recalculation based on discussion with FDA: following the discussion with FDA, the study will be deemed as successful if statistical significance is achieved in at least one of two levomilnacipran doses (40 mg/day and 80 mg/day) versus placebo based on the primary efficacy endpoint. Therefore, resultant sample size is **520** patients (**130** per treatment group) as required by 85% power based upon statistical significance in at least one of the two dose levels with the same effect size assumption.

[figure not shown]
Sample size recalculation based on interim analysis: following a blinded interim analysis, the sample size has been re-estimated. The MMRM model to estimate the pooled variance for change from baseline in CDRS-R total score at Week 8 includes pooled study site and week as factors and baseline CDRS-R total score and baseline value-by-week interaction as covariates, where week is included as a class variable. A total of 421 patients were included in the ITT analysis. Of these 421 patients, 347 (82.4%) patients have observed data at Week 8, so the estimated drop-out rate at Week 8 is 17.6%. Based on the MMRM model, the variance estimate for the change from baseline in CDRS-R total score at Week 8 is 129.53, and the estimated pooled standard deviation is 11.38. Thus the estimated effect size is 0.35 based on a treatment difference of 4 units and a pooled standard deviation of 11.38. Assuming an effect size of **0.35**, a common dropout rate of **17.6%**, and a correlation of 0.7 between the repeated measures, an estimated total sample size of **544** patients (**136** per treatment group) will be needed to maintain the 85% power to detect the treatment difference of 4 units for at least one levomilnacipran group versus placebo and for fluoxetine versus placebo.

15.0

STATISTICAL SOFTWARE

Statistical analyses will be performed using

[REDACTED]

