Assuming an effect size of 0.35, a common dropout rate of 17.6%, and a correlation of 0.7 between the repeated measures, an estimated total sample size of 544 patients (136 per group) will be needed to maintain the 85% power to detect the treatment difference of 4 units in at least 1 of the 2 doses of levomilnacipran versus placebo.

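### SAP 14.0 claims 85% power for fluoxetine versus placebo at 136 per group; its own inputs give about 79%, and at most 82.6% with no dropout

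*SAP*

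**What the plan says.** SAP section 14.0 gives three sample sizes in turn.

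- **660 patients (165 per group).** This provides 85% power for the levomilnacipran comparisons and for the "assay sensitivity analysis (fluoxetine vs. placebo"). The effect size of 0.36 "for both levomilnacipran and fluoxetine is based on a treatment difference of" 4 units, with SD 11.1, 17% dropout and correlation 0.7.
- **520 patients (130 per group).** After discussion with FDA, success is redefined as significance for at least one levomilnacipran dose. The 85% now refers to that criterion; fluoxetine is not mentioned.
- **544 patients (136 per group).** After the blinded interim analysis, "the estimated effect size is 0.35 based on a treatment difference of 4 units and a pooled standard deviation of 11.38". With 17.6% dropout and correlation 0.7, this number is said to maintain 85% "power to detect the treatment difference of 4 units for at least one levomilnacipran group versus placebo and for fluoxetine versus placebo".

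Protocol section 9.7.9 gives the same 544, but ties it only to "85% power to detect the treatment difference of 4 units in at least 1 of the 2 doses of levomilnacipran versus placebo". SAP section 10.0 sets the test level: "All statistical tests will be 2-sided hypothesis tests performed at the 5% level of significance for main effects".

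**The concern.** At 544 the SAP attaches one power figure to two criteria that differ. Success on at least one of two doses has two chances. Fluoxetine versus placebo has one. When the same 4-unit effect is assumed for every active arm, and the design is sized so that the first criterion has 85%, the second must have less. The fluoxetine clause fits the 660-patient design. It does not appear at the 520 step and returns at 544, although the new size was justified by the at-least-one criterion.

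The fluoxetine arm helps a reader decide what a negative levomilnacipran result means. If neither dose separates from placebo, a significant fluoxetine result points to the drug, and a non-significant one raises doubt about the trial. How much weight a non-significant result can bear depends on how often it would occur by chance when fluoxetine works as assumed. The SAP implies 15%; its inputs imply about 21%.

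**Working it through.** **Inputs.** From SAP 14.0: difference 4, SD 11.38 (variance 129.53), dropout 17.6%, correlation 0.7, n = 136 per group. From SAP 10.0: two-sided 5%. Fluoxetine is outside the gatekeeping family in SAP 10.2, so it gets the full 5%, which is the most favourable case. The effect size is 4/11.38 = 0.3515; the SAP rounds it to 0.35. Results below are for 0.3515, with 0.35 in brackets.

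**Formula.** z = effect size × √(n_eff/2); power = Φ(z − 1.960).

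**Effective n under the MMRM.** Patients who leave early still contribute through their earlier visits. Two simple cases can be checked by hand, assuming six postbaseline visits and equal correlation 0.7:

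- All dropout after the first visit: R² = 0.7² = 0.49. The information fraction is 1/(0.51/0.824 + 0.49) = 0.902, so n_eff = 122.6.
- All dropout just before Week 8: R² from five earlier visits = 5 × 0.49/(1 + 4 × 0.7) = 0.645. The fraction is 1/(0.355/0.824 + 0.645) = 0.930, so n_eff = 126.4.
- Dropout spread evenly lies between: fraction 0.921, n_eff = 125.2.

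**First, the plan's own figure.** The Simes rule for two doses rejects at least one if the smaller p is at most 0.025 or both are at most 0.05. The two dose statistics share the placebo group, so their correlation is 0.5. With z = 2.781 (even dropout) the power for at least one dose is 85.8% (85.5%). The range over the two extreme dropout timings is 85.1% to 86.1% (84.8% to 85.8%). The intersections with CGI-S are left out and can only lower this. The same method gives 86.0% for the 520 step (effect size 0.36, 17% dropout). Both agree with the stated 85%.

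**Fluoxetine versus placebo at 136 per group.**

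| Case | n_eff | z | Power |
|---|---|---|---|
| No dropout | 136 | 2.898 | 82.6% (82.3%) |
| MMRM, dropout just before Week 8 | 126.4 | 2.794 | 79.8% (79.5%) |
| MMRM, even dropout | 125.2 | 2.781 | 79.4% (79.1%) |
| MMRM, dropout after first visit | 122.6 | 2.752 | 78.6% (78.3%) |
| Completers only, 136 × 0.824 | 112.1 | 2.631 | 74.9% (74.5%) |

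The first row does not depend on the number of visits, the correlation or the timing of dropout.

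**Where 85% did hold.** At 165 per group with effect size 4/11.1 and 17% dropout, fluoxetine power is 84.7% on completers (n_eff 136.9) and 88.2% under the MMRM (n_eff 152.4).

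**The reverse check.** A single comparison with 85% power needs z = 1.960 + 1.036 = 2.996. At that z, power for at least one dose would be 90.5%, not 85%. The n per group is 2 × (2.996/0.3515)² = 145.3, so 146 with no dropout. Dividing by 0.921 gives 158, and by 0.824 gives 177. With 0.35 these become 147, 160 and 178.

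**The case against.** **The SD may be too large.** The blinded model has no treatment term, so 11.38 may include differences between arms. If all three active arms differ from placebo by 4 units, the between-arm variance is 16 × ¾ × ¼ = 3, and the SD is √(129.53 − 3) = 11.25. Fluoxetine power is then 80.3% under the MMRM and 83.5% with no dropout. The point is fair, but the figure stays below 85%.

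**Baseline adjustment adds power.** It does, but it is already counted. The model behind 11.38 has "baseline CDRS-R total score and baseline value-by-week interaction as covariates, where week is included as a class variable".

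**The 79% rests on assumptions.** The number of visits, equal correlation and the timing of dropout are not in the documents that can be read, and the plan's figures come from a simulation whose details are not shown. This stands as a caution about the exact replacement figure. It does not rescue the claim, because the no-dropout ceiling needs none of these assumptions.

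**At-least-one power is not always higher.** True: the comparison above assumes 4 units for both doses. But the method reproduces the SAP's 85% on exactly that assumption.

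**It changes nothing confirmatory.** Fluoxetine is outside the family of tested hypotheses, 544 rests on levomilnacipran alone, and no visible rule ties a non-significant fluoxetine result to calling the trial failed. The final estimate and its interval will carry more weight than planned power. All of this stands and limits the consequence. The protocol is silent on fluoxetine at 544 rather than in conflict with the SAP. A stated power that the design does not have still needs correcting.

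**Conclusion.** The concern holds. On the SAP's inputs, 136 per group gives about 79% power for fluoxetine versus placebo (78.3% to 79.8% over dropout timing and rounding of the effect size), against a stated 85%. The shortfall is about 6 points under the MMRM and at least 2.4 points (85 − 82.6) with SD 11.38 taken as given; even with the SD reduced to 11.25 the no-dropout ceiling is 83.5%. The 79% assumes six postbaseline visits, equal correlation of 0.7, monotone dropout of 17.6% and a true fluoxetine effect of 4 units. The 85% for at least one levomilnacipran dose is reproduced and is not in question.

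**What to change.** In SAP 14.0, limit the 85% statement at 544 patients to at least one levomilnacipran dose versus placebo, as Protocol 9.7.9 does. Add a separate sentence giving the power for fluoxetine versus placebo at 136 per group: about 79% at two-sided 5% under the same assumptions, with a range of 75% (completers only) to 83% (no dropout). If the sponsor can rerun its simulation for that comparison, report that value and its visit and dropout assumptions instead.

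The cost is one or two sentences and a less favourable stated figure. Sample size, tests, models and populations do not change.
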